4.3 Recruitment and retention strategies

Community mobilization and microfinance group engagement: AMPATH staff from Family Preservation Initiative (FPI), GESPs (community supervisors of GISHEs) and Harambee project personnel will conduct community mobilization meetings with microfinance group leaders to inform them about the study and randomization process. Additionally, research personnel will complete a mapping exercise during project Year 1 to assess feasibility of group engagement and willingness to participate. Only after obtaining acceptance from the groups for the study's community entry will groups be approached to complete enrollment procedures and baseline assessments.

Participant recruitment and retention in microfinance groups: FPI staff who have long-standing relationships with many of the MF group leaders will work with the investigative team in Kenya to recruit as many members as possible during the enrollment period. The intervention will be provided when more than half of the group members agree to participate. Microfinance group members who do not wish to participate will not be excluded from any ongoing microfinance group activities.

Attending microfinance group meetings is on its own an incentive for retention in care since care will be provided in conjunction with the on-going routine meetings where participants buy shares and take turns borrowing money from a common savings pool. By combining care with microfinance, financial

incentives are built into the structure of this local, grassroots activity, and thus will not be expected to require long term (external) donor support to be sustainable.

In the MF + ICB groups (Study Arm A), we anticipate that the community-based care intervention itself will be a substantial incentive for attending study visits and for ongoing study participation.

Additionally, the following factors will also serve to increase participant retention in Study Arms A and B:

- Microfinance is a strong motivator for participation, regardless of whether participants receive community- or facility-care
- The social network created by the microfinance groups is a good source of information such that peers will play an active role in recruitment and retention efforts
- Our previous community-based care interventions show that participation and retention rates are high because participants' need for transportation to and from a clinical site is minimized (Arm A)
- The study assessments will be conducted at community locations that are convenient for participants
- We will hire appropriately-trained staff members to conduct recruitment and retention activities; many staff members have already been working with the MF groups for a number of years

Participant retention in the SOC arm: Research personnel will attempt to contact identified eligible SOC participant up to 2 times to invite them to enroll in Aim 1. Research personnel will attempt to contact each enrolled SOC participant up to two times to complete the 18-month follow up assessment (i.e., viral load and surveys). In the event that a participant cannot be located, their most recent viral load measurement will be ascertained from the patient's AMRS data to estimate viral suppression at 18 months.

5. Aim 1 RCT Methods: Randomization ⁴

Group randomization will occur after all consenting participants complete baseline assessments using a computer-generated sequence to randomize MF groups to receive either integrated community-based care (ICB) or standard of care. The randomization process will be conducted centrally by biostatisticians at Brown University.

6. Aim 1 RCT Methods: Intervention Delivery ⁵

Integrated care visits will occur monthly during months 1-6 of the trial, and then quarterly for the remaining months (7-18). Initial intervention group visits (months 1-6) will focus on acute non-HIV related needs and screening for NCDs, such as diabetes and hypertension. Facilities will be informed that participants will be receiving HIV care outside of clinic for the duration of the study, unless additional care is required (i.e., referral to facilities for worsening HIV, acute care, hospitalization, etc.). Protocols

⁴ See the Addendum to the overall project protocol starting on page 100 for changes made to the randomization process.

⁵ See the Addendum to the overall project protocol starting on page 100 for changes made to the schedule and format of intervention delivery.

for handling new opportunistic infections, suspected viral resistance, malignancy screening and diagnosis will follow established AMPATH care protocols.

Prior to each intervention visit in the community, the clinical officer will review patient medical records to confirm each microfinance group members care needs at the upcoming visit. If an ART refill is needed at the upcoming visit, the clinical officer will work with the AMPATH pharmacist to prepare the ART medications and package them in a brown paper bag. If a NCD medication refill is needed at the upcoming visit, the clinical officer will work with the AMPATH pharmacist to prepare the NCD medication and package them in a brown paper bag.

The study intervention (Study Arm A) will deliver integrated care for HIV, diabetes, and hypertension in the community to enrolled microfinance group members during regularly scheduled GISHE group meetings. The intervention will include the following components (Figure 2):

(1) a one-on-one clinical consultation between an AMPATH clinical officer and a microfinance group member, during which the clinical officer will conduct vital signs screening, perform an HIV-related clinical evaluation, perform an NCD-related clinical evaluation, distribute prepackaged antiretroviral therapy for HIV, and distribute pre-packaged medications for diabetes and hypertension, as needed.

[figure not shown]
6.1 Medication refills

[figure not shown]
- All antiretroviral therapy will be provided to microfinance group members free of charge in accordance with AMPATH care protocols and national policies.
- NCD medication costs will be charged to the patient following the discounted costs set by the Kenya Medical Supplies Agency (KEMSA). The cost(s) of NCD medications during ICB care visits will be the same as the NCD medication costs at the AMPATH facility. The amount of NCD medications packaged and brought to the community visit will be enough to last until the next integrated care visit. Each NCD patient will be allowed to buy the quantity of NCD medication they can afford at the time of the visit (i.e., the entire refill or only a portion of the refill). If a given patient chooses to purchase only a portion of their NCD refill, the clinician will give the patient a prescription for the remaining quantity that the patient can then choose to fill at a pharmacy prior to the next integrated, community care visit. After each ICB care visit the clinician will take back all remaining drugs, as well as any and all funds received from NCD medication refills. A written receipt will be given to each patient who purchased a supply of NCD medication, and a copy of the receipt will be taken back to facility and entered into the Revolving Fund Pharmacy records.

6.2 Point of care testing

• Viral load testing: The most recent viral load test result available in the patient's medical record with the 12 months prior to their enrollment date will serve as the patient's baseline viral load. If no test result is available, no viral load test result will be performed. For all microfinance group members in the integrated care arm, study staff will collect a blood sample during the 18-month study visit in the community to measure endline viral load and assess the study's primary outcome. AMPATH care protocols require PLWH to receive a viral load test every 12 months such that some patients may have an additional viral load test result in their medical record during the middle of the trial. These results will not be used in the effectiveness analyses.

Figure 2. Harambee Study Clinical Flow (Study Arm A) Updated May 09, 2021

VL = viral load; LDL = undetectable viral load; BP = blood pressure; Tx = treatment; Dx = diagnosis; RBS = random blood sugar; Cr = creatinine; DKA = diabetic ketoacidosis; HHS = hyperosmolar hyperglycemic state; mth=month; prn= pro re nata ("as needed").

- Creatinine test: A creatinine test will be conducted among all microfinance group members in the integrated care arm during the baseline visit in the community and during the final 18-month visit in the community. The baseline and endline tests will be sponsored by the study and conducted using Creatinine cartridges and a point-of-care iStat machine that the study team will be responsible for transporting to the group meeting location. The clinical officer may recommend a patient seek additional creatinine tests at a facility during the trial, which will be charged to the patient.
- Random blood sugar (RBS): A random blood sugar test will be conducted among all microfinance group members in the integrated care arm during the baseline visit in the community and during the final 18-month visit in the community. The baseline and endline tests will be sponsored by the study and conducted using a glucose strip and glucometer that the study team will be responsible for transporting to the group meeting location. The clinical officer may recommend a patient seek additional creatinine tests at a facility during the trial, which will be charged to the patient.
- HbA1C test: A hemoglobin A1C test will be conducted among all microfinance group members in the integrated care arm during the baseline visit and during the final 18-month visit in the community if their RBS > 7.8 mmol/L or if their FBS > 6.1 mmol/L. The baseline and endline tests will be sponsored by the study.
- Systolic and diastolic blood pressure will be assessed during each clinical evaluation conducted in the community using a routine blood pressure cuff.
- (2) one-on-one referrals of the patient by the clinical officer to a health facility for emergency or acute care needs that cannot be addressed in the community (i.e., becomes virally unsuppressed/viremic, presents with new opportunistic infection, is lost to follow up, has moved out of study county, or another reason).
- (3) group-level health education during which the clinical officer will discuss positive HIV management habits, and health lifestyle habits for managing chronic conditions, and GISHE group members will be able to ask questions together.

For one-on-one activities, each participant will be invited to a private location near their group meeting location (e.g., private room in a community hall, empty classroom in an empty school) to meet with the clinical officer. For group-level health education activities, groups will convene in their regular GISHE meeting location (e.g., in an empty community hall, outdoors away from other crowds).

Clinical encounter data, medication distribution data and data on referrals will be recorded in REDCap in the community and then transferred to the patient's medical record by the clinical officer when the clinical officer returns to the facility.

- 7. Aim 1 RCT Methods: Data collection, management, and analysis
- 7.1 Data Collection

The trial involves the collection and use of the following types of data. With the exception of viral load data which will be ascertained from and/or entered directly into patient medical records, data will be collected using mobile tablets with secure encryption and cloud-based data capture.

1. We will measure HIV viral load at study enrollment and at 18-months for all enrolled trial participants.

- 1.1 Baseline viral load will reflect the most recent viral load measurement available in the patient's medical record within the 12 months prior to their enrollment date.
- 1.2 18-month viral load will be assessed using blood draws taken during the 18-month assessment in the community (for microfinance group members) and at the facility (for non-microfinance group members).
- 2. For clinical secondary outcomes, we will measure systolic blood pressure and hemoglobin A1c at baseline and 18-months for all 900 microfinance group members enrolled in the trial. Blood pressure will be measured in the community by the clinical officer using a blood pressure arm cuff. HbA1c will be measured in the community by the clinical officers using a point of care test.
- 3. For non-clinical secondary outcomes, we will measure retention in care on an ongoing basis for all enrolled trial participants. Retention in care will be based on study records (REDCap) for intervention recipients and on medical records for facility care patients.
- 4. For exploratory outcomes and mediation analyses, we will collect survey data from all enrolled trial participants: at enrollment and 18-months for all trial participants, with an additional round of survey data collection at month 9 for all microfinance group members. Surveys will be administered by a research assistant to participants in a private location in-person. Surveys will assess demographics, health insurance enrollment and utilization, social support (Oslo Social Support Scale-3), quality of life (adapted version of the MOS-HIV scale), psychological distress (Patient Health Questionnaire-4), self-reported ART adherence (based on the adapted ACTG Adherence Questionnaire), self-reported adherence to NCD medications (based on the extent of DOSE-Nonadherence Questionnaire), barriers to accessing care, patient satisfaction with care, felt HIV stigma (9-item measure of felt stigma validated in Kenya). The survey instrument is included in Appendix III. For exploratory outcomes, we will collect data on microfinance group performance (e.g., saving and lending activities, loan default rates) for all microfinance group participants. Microfinance group performance data will be collected on a quarterly basis and recorded via REDCap. The microfinance data collection tool is included in Appendix IV.

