The Academic Model Providing Access to Healthcare (AMPATH) is based in western Kenya (~350km northwest of Nairobi) with primary headquarters in Uasin Gishu County, AMPATH is a joint partnership between Moi University School of Medicine, Moi Teaching and Referral Hospital, and a consortium of universities led by Indiana University and including Brown and University of Toronto. AMPATH has enrolled over 150,000 HIV+ patients in 156 Ministry of Health facilities in western Kenya. All HIV and tuberculosis (TB)-related care and treatment are free for patients. The HIV clinical care protocols used by AMPATH are consistent with WHO and Kenyan National (NASCOP) guidelines and entail routine 12-month viral load monitoring, with more intensive monitoring for unsuppressed patients. Care is supported and data are managed via AMPATH's electronic medical record system (AMRS). All care delivered in this study will be in line with clinical protocols in place within AMPATH. Moreover, AMPATH is already supporting more than 1349 MF groups (with over 27,249 people) as part of their Group Integrated Savings for Health Empowerment (GISHE) program and the Bridging Income Generation with Group Integrated Care (BIGPIC) randomized clinical trial.

Description of Study Manipulation:

A cluster randomized controlled design will be used to perform an Intervention/Experimental evaluation of integrated community-based care incorporated into existing microfinance groups, where all study participants are persons living with HIV (PLWH). Cluster randomization will be conducted at the level of existing GISHE groups and will be stratified by county.

> We will obtain informed consent from each individual participating in the trial, and randomize GISHE groups in a 1:1 ratio to receive either microfinance plus integrated community-based care for HIV, diabetes and hypertension (MF+ICB) or microfinance and standard facility-based care (MF+SOC).

> The intervention (MF+ICB) will be delivered within groups during regularly-scheduled microfinance group meetings and include the following: (1) integrated care visits by a clinical offer monthly during the first 6 months of the trial, and then quarterly for the remaining months (7-18), which will include one-on-one vital signs screening, consultation with a clinical officer, medication distribution (antiretroviral therapy for HIV

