- 5. The original project protocol stated that the *primary* endpoint was achievement of HIV viral suppression (HIV-RNA <400 copies/mL) at 18 months. The definition of the primary endpoint was changed such that patients whose 18-month viral load assessment was before January 1, 2023 were considered virologically suppressed if their viral load was <400 copies/mL, and patients whose 18-month viral load assessment was on or after January 1, 2023 were considered suppressed if their viral load was <200 copies/mL. This change to the primary endpoint definition was made to reflect changes to Kenya's national recommendations for HIV monitoring cutoffs that took effect in August 2022 during the active follow-up period.
- 6. The original project protocol stated that blood draws for viral load assessments (primary outcome) would be ascertained for all participants during their 18-month study visit. This protocol was revised such that if a participant had a viral load result available in their medical records within the 3 months prior to their 18-month assessment date, then this result was used to assess their 18-month viral load. This change was made to reduce burden on participants by preventing them from having to provide multiple blood samples within less than 6 months of one another, and to conserve administrative resources and phlebotomist effort.
- 7. The original project protocol stated that the secondary endpoints of (1) absolute mean change in systolic blood pressure and (2) absolute mean change in HbA1c level from 0 to 18 months would be assessed among all enrolled trial participants. This was revised such that the secondary endpoints of (1) absolute mean change in systolic blood pressure and (2) absolute mean change in HbA1c level were only assessed among members of randomized microfinance groups, and were not assessed among matched standard of care patients. This change was made primarily to reduce administrative and logistical burden on the research team. After beginning the matching process, many of the eligible, matched standard of care patients were patients of health facilities that were distinct from those where the majority of microfinance group members received care. For several matched patients, they were the only Harambee participant who was a patient of that health facility. Thus, the human

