Analysis plan for the primary objective: The analysis of the primary objective was conducted using a doubly robust generalized estimating equation with a logit link function accounting for potentially differential dropout as described in Prague M et al.⁷ The generalized estimating equation model included the intervention arm, used an independence working correlation matrix and the variance was estimated using a sandwich variance estimator for clustered data. The intervention effect was estimated using the log odds ratio coefficient of intervention in the generalized estimating equation. The primary hypothesis test of the intervention effect was conducted using a Wald test and 95% Wald-based confidence intervals were calculated.

Handling of dropout: Implementation of the method proposed in Prague M et al.⁷ relies on specifying a model for the dropout probability and two outcome models (one for each treatment arm). For the method to be a valid way to handle dropout, either the model for the dropout probability or both outcome models need to be correctly specified. The model used for the dropout probability was a logistic regression model with linear main effects of county, treatment arm, log(viral load at baseline+1)), schooling achieved, age, and gender. The model used for the outcome model in the MF+ICB was a logistic regression model with linear main effects of county, log(viral load at baseline+1)), schooling achieved, age, and gender and the model used for the outcome model in the MF+UC was a logistic regression model with linear main effects of county, log(viral load at baseline+1)), schooling achieved, monthly income, age, and gender. Monthly income was only used in one of the models due to instability of the model fitting when it was added to the other models. The dropout weights were well behaved with the largest weight being 1.42; therefore, we did not experience any extreme weights and hence made no adjustments to account for them.

Handling of missing data: Multiple imputation was used to account for missing data on baseline covariates and Rubin's rule for variance estimation was used for variance estimation.

⁷ Prague M, Wang R, Stephens A, Tchetgen Tchetgen E, DeGruttola V. Accounting for interactions and complex inter-subject dependency in estimating treatment effect in cluster-randomized trials with missing outcomes. *Biometrics*. Published online 2016. doi:10.1111/biom.12519

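### Routine mid-trial viral loads are barred from handling missing month-18 results as well as from the endpoint, and Section 4.3 contradicts that bar for Arm C

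*Combined protocol and SAP*

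**What the plan says.** Section 6.2 (Viral load testing) notes that, because care protocols call for a test every 12 months, "some patients may have an additional viral load test result in their medical record during the middle of the trial", and then rules: "These results will not be used in the effectiveness analyses". The Summary (Description of Sites) describes the care schedule as "routine 12-month viral load monitoring, with more intensive monitoring for unsuppressed patients".

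Addendum item 10 (Handling of dropout) gives the revised model: "The model used for the dropout probability was a logistic regression model with linear main effects of county, treatment arm", followed by log baseline viral load, schooling, age and gender. The two outcome models use baseline variables only, with monthly income added in one. Multiple imputation is confined to missing baseline covariates. The models for the secondary objectives have the same form. The baseline value may itself be old. Section 7.1 defines it: "Baseline viral load will reflect the most recent viral load measurement available in the patient's medical record within the 12 months prior to their enrollment".

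Two passages let routine results in as outcomes:

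- Addendum item 6 uses a record result as the month-18 value "if a participant had a viral load result available in their medical records within the 3 months prior to their 18-month assessment date".
- Section 4.3 (retention in the SOC arm) says that for an Arm C participant who cannot be located, "their most recent viral load measurement will be ascertained from the patient's AMRS data to estimate viral suppression at 18 months". It sets no time window.

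**The concern.** Keeping interim results out of the endpoint is sound, because their timing varies and unsuppressed patients are tested more often. Keeping them out of the missing-data model is a separate decision, and the plan gives no reason for it.

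The doubly robust estimator needs either a correct dropout model or two correct outcome models. Here all three are built from nearly the same baseline covariates. If viraemia arising after baseline drives both leaving and failure, both routes fail together. The stability analysis in Addendum item 10 varies polynomials and interactions of the covariates, so it cannot reveal this. A member found viraemic at month 8 and gone by month 18 is represented by remaining members with similar baseline data, most of them suppressed if suppression is as high as Addendum item 10 indicates.

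The separate rule for Arm C matters for the two secondary comparisons. There a missing month-18 result can be replaced by an old record value in one arm while it is weighted for in the other.

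**Working it through.** **Figures in the documents.** None gives the availability of interim results, their predictive strength, or dropout by interim status. Two related figures exist. Planned dropout is 15% (Section 3.4.2). The largest dropout weight is 1.42 (Addendum item 10); if a weight is 1/probability, the lowest fitted retention is 1/1.42 = 0.704. That describes weights fitted without the interim result.

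**Who should have a result.** Suppose the baseline test was k months before enrolment (k from 0 to 12) and testing is strictly annual. The next tests fall at months 12 - k and 24 - k. The first always falls in months 0 to 12, so anyone with a baseline result who stays in care is due an interim test by about month 12. The second falls in months 15 to 18, the window of Addendum item 6, only when k is between 6 and 9. Most annual results therefore lie outside that window. People who leave before their test have none.

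**Size, milder inputs (assumed).** Let u be the share unsuppressed mid-trial, s1 and s0 month-18 suppression after a suppressed and an unsuppressed interim result, d total dropout, and R the ratio of dropout in the unsuppressed to that in the suppressed.

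- Dropout if suppressed: d1 = d / [(1 - u) + uR]; if unsuppressed: d0 = R·d1.
- True rate: (1 - u)s1 + u·s0.
- Observed rate: [(1 - u)(1 - d1)s1 + u(1 - d0)s0] / (1 - d).
- Ranges: d 5-15%, u 5-10%, R 1.5-3, s1 97%, s0 50-70%.
- Upper corner (d = 0.15, u = 0.10, R = 3, s0 = 0.50): d1 = 0.125, d0 = 0.375; true 0.923; observed (0.763875 + 0.03125)/0.85 = 0.9354. Overstatement: 1.24 points.
- Lower corner (d = 0.05, u = 0.05, R = 1.5, s0 = 0.70): true 0.9565, observed 0.9568. Overstatement: 0.03 points.

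If such dropout occurred in one arm only, the A-B difference would move by up to 1.24 points.

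**Size, harsher inputs (assumed).** u 8-12%, s1 95%, s0 40%, dropout 8% if suppressed; if unsuppressed, 20-30% in A and 35-50% in B. Total dropout per arm is then 9.0% to 13.0%, below the planned 15%.

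Example with u = 0.12, 20% in A and 40% in B:

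- True rate: 0.88 × 0.95 + 0.12 × 0.40 = 0.884.
- A observed: (0.76912 + 0.0384) / (0.8096 + 0.096) = 0.892.
- B observed: (0.76912 + 0.0288) / (0.8096 + 0.072) = 0.905.
- A-B shift: -1.3 points.

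Over all corners:

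| Quantity | Smallest | Largest |
|---|---|---|
| Overstatement per arm | 0.5 (u = 8%, dropout 20%) | 2.8 (u = 12%, dropout 50%) |
| A-B shift | -0.2 (u = 8%, 30% v 35%) | -2.0 (u = 12%, 20% v 50%) |

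The shift is zero if viraemic members leave equally in both arms, and changes sign if they leave more in A. Both sets of figures are unadjusted complete-case rates, so they ignore whatever the baseline covariates already correct.

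**Does the fix help with incomplete testing?** Take the same example and assume that half of leavers and 90% of completers have an interim result. Within an arm, each category is weighted by (retained + left)/retained. In B the weights are 1.05 (suppressed), 0.0888/0.0648 = 1.37 (unsuppressed) and 0.14736/0.08816 = 1.67 (none recorded). The estimate is 0.76384 × 0.95 + 0.0888 × 0.40 + 0.14736 × 0.9051 = 0.8945, so the bias falls from 2.1 to 1.05 points. In A it falls from 0.77 to 0.38. The A-B shift is halved, from -1.3 to -0.7.

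**The case against.** Baseline covariates are a common choice for a dropout model, and no document calls the interim result a strong predictor. Section 6.2 says only that some patients will have one, and leavers are the least likely to. Section 7.1.2 has staff arrange separate meetings for microfinance members who miss the month-18 session, and more intensive monitoring makes it likelier that viraemic patients still in care have a result inside the 3-month window. A category for no recorded result is partly a marker of early departure and could carry large weights. The analysis is reported as complete, so replacing the primary dropout model now would be a late change. All of this stands. It limits the size of the point and argues for a sensitivity analysis. It does not explain why a recorded predictor should be left out altogether.

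Two stronger readings should be resisted. A reader might infer that the protocol expects viraemic members to be kept better in Arm A, so that the bias runs against the intervention. Section 4.3 expects good retention in Arm A generally, because travel is reduced, and says nothing about viraemic members. Sections 3.2 and 6.2 refer Arm A members who become viraemic to a facility, while the month-18 draw is in the community, which could work the other way. A reader might also infer that adding the interim result would remove the bias. That holds only if every leaver had been tested.

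**Conclusion.** The gap is real and moderate. For Arm A against Arm B, no viral load recorded between enrolment and about month 15 enters the weights, the outcome models or the imputation, and neither double robustness nor the stability analysis makes up for that. The bar is not total: Addendum item 6 admits late results, and Section 4.3 admits results of any age for unlocated Arm C participants. The latter contradicts Section 6.2 and makes outcome ascertainment differ by arm.

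The likely size is about 1 point or less per arm when suppression is high, with larger values only under the harsher inputs. A shift in A-B needs unequal dropout of viraemic members, for which the documents give no evidence, so its direction is uncertain. The documents do not show that the reported result is biased; they show that the plan cannot tell.

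**What to change.** 1. Reword Section 6.2: routine follow-up viral loads do not define the month-18 endpoint, except as Addendum item 6 allows, but may inform the handling of its missingness.
2. Reconcile Section 4.3 with Section 6.2 and Addendum item 6, so that one rule for the month-18 outcome applies in all arms. Until then, the same Arm C result could serve as both outcome and dropout predictor.
3. Beside the primary analysis, add a sensitivity analysis that puts the last viral load recorded between enrolment and month 15 (suppressed, unsuppressed, none recorded), with its interaction with arm, into the dropout models for the primary and secondary objectives. Leave the endpoint and the baseline-covariate outcome models as they are.
4. Report by arm the share with an interim result, among completers and leavers, and the resulting range of weights.

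The cost is one extraction from records that participants have already consented to share, plus a change of wording. The weights will spread more widely, protection for this covariate will rest on the dropout model alone, and correction will be partial. Testing may also differ between community and facility care, which is a further reason to keep this as a sensitivity analysis.
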